3.3 Determination of Sample Size

The sample size calculation is based on demonstrating superiority of quinagolide vaginal ring compared to placebo vaginal ring on the primary endpoint of changes in the sizes of endometrioma, DIE and adenomyosis lesions summed by type on MRI at cycle 4. An important assumption behind the sample size calculation is an equal magnitude of treatment effect for all three types of lesions. For example, for adenomyosis, by assuming an average baseline lesion size of 18 mm and a standard deviation of 4.5 mm [1], a sample size of 24 randomised subjects (16 on active treatment and 8 on placebo) will have 83% power to detect a treatment effect difference of 6 mm (corresponding to a 33% reduction in lesion size) using a two-sample t-test at a 5% two-sided significance level. A similar assumption, i.e. the ratio between treatment effect and standard deviation is 4 to 3, is made for DIE and endometrioma to conclude 24 subjects to be randomised per sub-group. In total, 72 subjects will be randomised in this trial.

Table 3-2 Sample Size by Treatment Effect Difference

Difference in the sum of lesion size reduction between quinagolide vaginal ring group and placebo vaginal ring group		Number of subjects in total ^a	
Absolute difference (mm)	Relative difference ^b (%)	Power 80%	Power 90%
4.5	25	39	51
5.0	28	33	42
5.5	31	27	36
6.0	33	24	30
6.5	36	21	27
7.0	39	18	24
7.5	42	15	21

a Using a 2:1 randomisation and assuming a standard deviation of 4.5 mm.

b Assuming an average baseline lesion size of 18 mm.

If the drop-out rate in any of the sub-groups are larger than 10%, the sample size of randomised subjects for that sub-group may be increased to up to 30.

The study was planned to be have a randomisation ratio of 2:1 with 2 subjects receiving quinagolide vaginal ring for each subject receiving placebo vaginal, however it was discovered, after LPLV but before database lock, that the randomisation list used during the study had a 1:1 ratio between quinagolide vaginal ring placebo vaginal ring. The use of a 1:1 ratio instead of a 2:1 ratio will increase the power to detect a difference between quinagolide vaginal ring and placebo vaginal ring.

4 Subject Disposition

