9.1 General Considerations

All efficacy endpoints will be summarised using descriptive statistics and will be performed by treatment and in total for each of the three types of lesion (endometrioma, DIE and adenomyosis), for endometriosis (endometrioma and DIE), and for the three types of lesions combined.

Categorical data will be summarised using numbers and percentages (n and % of all observed) in addition to the sum ‘All’, the percentages are based on the total number of subjects with a corresponding assessment in the analysis set. Continuous data will be presented, using the number of subjects (n), mean and standard deviation, median, 25th percentile, 75th percentile, minimum, and maximum, unless otherwise specified.

All statistical tests will be performed using a two-sided test at a 5% significance level. Treatment differences will (where appropriate) be presented with 95% confidence intervals and p-values corresponding to the statistical test of the hypothesis of “equal effect” against the alternative of “different effect”.

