Secondly all monotone missingness is imputed, using a standard MAR based MI approach for monotone missingness, which imputes variables one at a time in the following order: the overall NRS score at visit 2, at visit 5, at visit 6, at visit 7, and at visit 8, and finally the sum of lesion sizes at end-of-treatment.

For each type of lesion and each imputation, the primary endpoint will be analysed using an analysis of covariance (ANCOVA) model, with the change in the sum of lesion sizes from baseline measured at end-of-treatment as the dependent variable, the baseline sum of lesions as covariate, and the treatment group as fixed effect. The treatment difference between active treatment versus placebo will be estimated for each of the three types of lesions.

Finally, the 100 different imputations are combined to an estimate of the treatment difference between active treatment versus placebo and its 95% confidence interval and corresponding p-value using SAS Proc Mianalyze.

In order to control the overall type I error at 5%, the Hochberg procedure is implemented by ranking the 3 p-values in a decreasing order. If the largest p-value is ≤ 0.05 , superiority is established for all 3 types of lesions. If the largest p-value is > 0.05 , but the middle p-value is ≤ 0.025 , superiority is established for the two types of lesions with the smaller p-values. If the largest p-value is > 0.05 and the middle p-value is > 0.025 , but the smallest p-value is ≤ 0.0125 , superiority is established for only the type of the lesion with the smallest p-value. If the largest p-value is > 0.05 , the middle p-value is > 0.025 , and the smallest p-value is > 0.0125 , superiority is not established for any of the 3 types of lesions.

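### SAP 9.2.1 pools the primary ANCOVAs with Proc Mianalyze without specifying complete-data degrees of freedom; when few MRIs are missing, the p-values come out too small and the intervals too short

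*SAP*

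**What the plan says.** SAP 9.2.1 imputes a missing end-of-treatment sum of lesion sizes 100 times. The regression uses treatment, baseline sum and the overall NRS score at visits 2, 5, 6, 7 and 8. Each completed data set is analysed by an ANCOVA with baseline sum and treatment; SAP 12 explains why site was dropped. The 100 results are combined into an estimate with "its 95% confidence interval and corresponding p-value using SAS Proc Mianalyze". Neither the SAP nor the protocol says which df the pooled test uses.

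The three p-values then enter a Hochberg procedure with cut-offs 0.05, 0.025 and 0.0125, whose stated purpose begins "In order to control the overall type I error at 5" per cent. SAP 3.3 plans each sub-group as "a sample size of 24 randomised subjects (16 on active treatment and 8 on placebo"), with power computed "using a two-sample t-test at a 5% two-sided significance level". It also reports that the "randomisation list used during the study had a 1:1 ratio". SAP 3.2 lets a woman count in more than one lesion type.

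SAP 9.2.2.2 adds two ANCOVAs per lesion type without imputation.

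**The concern.** When an analysis set is small, a pooled multiple-imputation test needs a df that reflects its size. Rubin's large-sample df depend only on the number of imputations and the fraction of missing information. They take the complete-data df as infinite. With 100 imputations and few missing MRIs, the test is in effect referred to a normal distribution, although the residual variance is estimated from about two dozen women.

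The primary p-values and confidence intervals are at stake, and so is the 5% family-wise control that 9.2.1 sets out to provide. The relative distortion grows at the stricter cut-offs, where a single lesion type would be declared a success.

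It can also produce an odd result. If no MRI is missing, the primary analysis and the ANCOVA without imputation use identical data and give the same t statistic. At 21 df, t = 2.08 gives p = 0.05 in the unimputed ANCOVA and about 0.038 against a normal reference. The primary analysis would then be more liberal than its own sensitivity check.

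**Working it through.** **Inputs from the SAP.** Two-sided 5% (9.1). Planned n = 24 per sub-group, difference 6 mm, SD 4.5 mm, allocation actually used 1:1 (3.3). Imputations m = 100, eight imputation coefficients including the intercept, and ANCOVA with intercept, baseline and treatment (9.2.1). Complete-data df are therefore n − 3 = 21 at n = 24.

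**The plan's own figure.** For 16 versus 8, the noncentrality is (6/4.5) × √(16 × 8/24) = 3.08 on 22 df. This gives power 83.7% against 83% stated, and every row of Table 3-2 reproduces. A normal approximation gives 86.8%, so the plan itself used a t reference at this sample size.

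**Degrees of freedom.** Let λ be the fraction of total variance due to missing data.
- Large-sample: ν = (m − 1)/λ².
- Barnard-Rubin: ν_obs = [(ν₀ + 1)/(ν₀ + 3)] ν₀ (1 − λ), then 1/ν_BR = 1/ν + 1/ν_obs, with ν₀ = 21.

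| λ | Large-sample df | Critical value | Barnard-Rubin df | Critical value |
|---|---|---|---|---|
| 0.05 | 39,600 | 1.960 | 18.3 | 2.099 |
| 0.10 | 9,900 | 1.960 | 17.3 | 2.107 |
| 0.20 | 2,475 | 1.961 | 15.3 | 2.128 |

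Example at λ = 0.10: 99/0.01 = 9,900; (22/24) × 21 × 0.9 = 17.3.

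**Limit with no missing MRI.** The true level is 2·P(t₂₁ > z):
- nominal 5%, 2.5% and 1.25% become 6.3%, 3.6% and 2.1%;
- interval length ratio 1.960/2.080 = 0.942, so 5.8% too short, with coverage 93.7%;
- the 5% test at other sizes: 6.9% (n = 18), 6.0% (n = 30), 5.9% (n = 36), 5.8% (n = 40).

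The family-wise error for three independent nulls with cut-offs 0.05/0.025/0.0125 at 21 df is 6.2% with a normal reference and 3.8% with t.

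**With missing MRIs.** The null simulation used the SAP's eight-coefficient imputation model, 12 per arm, m = 100 and 40,000 trials per row (Monte Carlo error about 0.1 point on the 5% test). Assumptions not in the documents: normal data, baseline-outcome correlation 0.6, NRS correlation 0.3, NRS complete, MRIs missing completely at random.

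| Missing of 24 | 5% test, large-sample df | 5% test, Barnard-Rubin df | 1.25% test, large-sample df |
|---|---|---|---|
| 0 | 6.3% | 4.8% | 1.98% |
| 1 | 5.8% | 4.3% | 1.79% |
| 2 | 5.4% | 3.9% | 1.64% |
| 3 | 5.0% | 3.6% | 1.55% |
| 5 | 4.3% | 2.9% | 1.26% |

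Smaller runs with other seeds and correlations scatter around these values, for example 5.0% to 6.0% at two missing with large-sample df.

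**Family-wise error with missing MRIs.** Nearly all of it comes from the smallest p-value, so 1 − (1 − a)³ with a from the last column is a close lower figure: 5.3% at one missing, 4.8% at two (about 4.9% with the other Hochberg steps), 4.6% at three and 3.7% at five.

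**The case against.** The strongest reply is that a reader might infer more than the documents support, in four ways.

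- **That the SAP chose infinite df.** It did not; it is silent. No program code is in the documents, and the outcome turns on an option that may yet be set. This stands. But the SAP fixes the software, the number of imputations and the imputation order, and two programmers following it could still report different primary p-values.
- **That 5% is exceeded whatever happens.** The imputation model spends eight coefficients on about 20 observed women, which inflates between-imputation variance and offsets the wrong reference. Simulating without the NRS scores gives 5.9% to 6.5% at 2 to 5 of 24 missing, but that is not the model in 9.2.1. This stands too, and it limits the excess to low missingness.
- **That family-wise control is lost.** The last cut-off, 0.0125, is stricter than 0.05/3 and absorbs part of the excess. This is true of the text as written, but it is not a designed safeguard. With 0.05/3 the no-missing figure would be about 7.7% with a normal reference, against 5.0% with t.
- **That 24 women are analysed per type.** The FAS for endometrioma or DIE takes every treated woman with a qualifying lesion of at least 10 mm, and the sets overlap. They may be larger or smaller than 24.

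The ANCOVAs without imputation would expose a result that rests only on the df, but they do not feed Hochberg.

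Low missingness is not remote. The 10% drop-out trigger in SAP 3.3 corresponds to 2.4 of 24, and women who stop during or after cycle 2 are still asked for an MRI.

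**Conclusion.** The point holds as a conditional defect of moderate severity. SAP 9.2.1 leaves the pooling df unspecified. If none is supplied, the reference distribution is wrong for sets of this size.

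At n = 24 with no missing MRI, the per-test level is 6.3% instead of 5%, the interval is 5.8% too short and the family-wise error is about 6.2%. Under the SAP's imputation model the per-test excess is about 0.6 to 0.9 points at 1 of 24 missing. At 2 it is 0.4 points in the largest run and at most about 1.0 in the others. By about 3 to 4 it is gone, and the family-wise error is then near or below 5%. Larger sets reduce it: about 5.9% per test at n = 36 with nothing missing.

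The no-missing per-test figures are exact under normality. The others rest on the simulation assumptions listed above, and the family-wise figures also on independent lesion-type tests. The behaviour of the procedure when no df is given is a property of the software and is not stated in the documents. They do not support saying that the 5% level is exceeded in general.

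**What to change.** Add one sentence to SAP 9.2.1, before unblinding: imputations are pooled with Barnard-Rubin small-sample df, with the EDF option of Proc Mianalyze set to the residual df of the ANCOVA in that analysis set (n − 3). Apply the same rule wherever imputations are pooled in 9.2.2, 9.2.3 and 9.3.1 to 9.3.3. In 9.2.2.5 the added yes/no factor for previous hormonal treatment makes it n − 4.

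The cost is one sentence and one program option. Intervals widen by about 6% or slightly more at n = 24. The test becomes mildly conservative when some MRIs are missing: about 3% to 4% at 2 to 4 of 24, against 4.8% with none. That is a real loss in a small phase 2 trial, but the rule keeps each test at or below its nominal level in every 12-per-arm setting of the 40,000-trial simulation.

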9.1 Determination of Sample Size

The sample size calculation is based on demonstrating superiority of quinagolide vaginal ring compared to placebo vaginal ring on the primary endpoint of changes in the sizes of endometrioma, DIE and adenomyosis lesions summed by type on MRI at cycle 4. An important assumption behind the sample size calculation is an equal magnitude of treatment effect for all three types of lesions. For example, for adenomyosis, by assuming an average baseline lesion size of 18 mm and a standard deviation of 4.5 mm,³⁹ a sample size of 24 randomised subjects (16 on active treatment and 8 on placebo) will have 83% power to detect a treatment effect difference of 6 mm (corresponding to a 33% reduction in lesion size) using a two-sample t-test at a 5% two-sided significance level. A similar assumption, i.e. the ratio between treatment effect and standard deviation is 4 to 3, is made for DIE and endometrioma to conclude 24 subjects to be randomised per sub-group. In total, 72 subjects will be randomised in this trial.

Table 9-1 summarises the required sample size in total for different assumptions of treatment effect difference and power.

Table 9-1 Sample Size by Treatment Effect Difference

Difference in the sum of lesion size reduction between quinagolide vaginal ring group and placebo vaginal ring group		Number of subjects in total ^a	
Absolute difference (mm)	Relative difference ^b (%)	Power 80%	Power 90%
4.5	25	39	51
5.0	28	33	42
5.5	31	27	36
6.0	33	24	30
6.5	36	21	27
7.0	39	18	24
7.5	42	15	21

^a Using a 2:1 randomisation and assuming a standard deviation of 4.5 mm.

^b Assuming an average baseline lesion size of 18 mm.

If the drop-out rate in any of the sub-groups are larger than 10%, the sample size of randomised subjects for that sub-group may be increased to up to 30.

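### The last Hochberg step is set at 0.0125 (0.05/4) instead of 0.0167 (0.05/3), and the 83% power takes no account of the Hochberg rule

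*SAP*

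**What the plan says.** SAP 9.2.1 states: "In order to control the overall type I error at 5%, the Hochberg procedure is implemented" by "ranking the 3 p-values in a decreasing order". The steps follow. "If the largest p-value is ≤ 0.05", all three types are declared superior. Otherwise, if "the middle p-value is ≤ 0.025", the two types with the smaller p-values are. Otherwise, if "the smallest p-value is ≤ 0.0125", only the type with the smallest p-value is. The closing sentence, on when nothing is established, repeats 0.0125. Protocol 9.6.2 gives the same rule with the same three values, so 0.0125 stands twice in each document. The Protocol synopsis names Hochberg for the three primary analyses without giving thresholds.

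On power, SAP 3.3 states that "a sample size of 24 randomised subjects (16 on active treatment and 8 on placebo) will have 83% power" for a 6 mm difference with SD 4.5 mm, using a two-sample t-test at a two-sided 5% level. Protocol 9.1 says the same. The 4-to-3 ratio of effect to SD is carried over to the other two types. Neither section mentions the Hochberg rule. SAP 3.3 and section 12 add that the randomisation list actually used was 1:1 and that this raises power, but give no figure.

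**The concern.** Hochberg divides alpha by 1, 2, 3 and so on as it steps down from the largest p-value. The first two written thresholds follow that pattern. The third skips to 0.05/4, which belongs to a family of four hypotheses. The named method and its written steps can therefore give different verdicts on the same data, and they do so in the primary success rule. An analyst running a standard Hochberg routine would contradict the SAP text whenever the smallest p-value falls in the gap.

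The last step decides the result when only one lesion type responds. Protocol 3.5.1 says the three-sub-group design should help identify the type that responds best, so this case matters to the trial's purpose.

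The power statement is a related, lesser matter. A reader will take 83% as the chance of establishing superiority for a given type, yet success is judged by the Hochberg rule and not by one test at 5%.

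**Working it through.** **Inputs.** Overall alpha 5%, Hochberg, three p-values (SAP 9.2.1, Protocol 9.6.2). Per type: 24 subjects split 16:8, difference 6 mm, SD 4.5 mm, two-sided two-sample t-test at 5% (SAP 3.3, Protocol 9.1). Equal effect/SD of 4/3 in all types (same sections). Actual list 1:1 (SAP 3.3), taken here as 12:12. Independence of the three tests is my assumption.

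**1. The plan's own figure.** Noncentrality = 6 / (4.5 × √(1/16 + 1/8)) = 6 / 1.949 = 3.08 on 22 df. Power at two-sided 0.05 is 83.7%, which agrees with the stated 83%. The same formula at 0.05 reproduces all 14 sample sizes in Protocol Table 9-1 and SAP Table 3-2. The planning calculation is therefore for one unadjusted test.

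**2. Thresholds for three hypotheses.**

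| Ordered p-value | Hochberg | As written |
|---|---|---|
| Largest | 0.05/1 = 0.05 | 0.05 |
| Middle | 0.05/2 = 0.025 | 0.025 |
| Smallest | 0.05/3 = 0.0167 | 0.0125 = 0.05/4 |

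**3. Familywise error under the global null.** Let c be the last threshold. Nothing is rejected when all three p-values exceed c, at most one lies in (c, 0.025], and at least one exceeds 0.05. With independent uniform p-values:

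P(no rejection) = (0.975³ − 0.025³) + 3(0.025 − c)(0.975² − 0.025²) = 0.92684 + 2.85(0.025 − c)

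- c = 0.0125: 0.92684 + 0.03563 = 0.96247, so the error is 3.75%.
- c = 0.0167: 0.92684 + 0.02375 = 0.95059, so the error is 4.94%.

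Simulation at 16:8 (1,000,000 trials) gave 3.74% and 4.93%. The corrected threshold still keeps the 5% level.

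**4. Power of one comparison at the last threshold** (noncentral t): 16:8 gives 64.1% at 0.0125 and 68.6% at 0.0167; 12:12 gives 70.4% and 74.4%. For 80% power at 2:1 in a type that must pass this step alone, the total is 33 subjects at 0.0125 and 30 at 0.0167, against 24 at 0.05.

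**5. Power of the full rule for a responding type** (1,000,000 simulated trials per scenario):

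| Split | Types responding | One test at 5% | As written | With 0.0167 |
|---|---|---|---|---|
| 16:8 | one | 83.7% | 64.7% | 68.9% |
| 16:8 | two | 83.7% | 72.3% | 73.4% |
| 16:8 | three | 83.7% | 80.4% | 80.6% |
| 12:12 | one | 87.7% | 70.8% | 74.7% |
| 12:12 | two | 87.7% | 78.3% | 79.1% |
| 12:12 | three | 87.7% | 85.6% | 85.7% |

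If all three types respond at 16:8, the chance of at least one success is 96.7% as written and 97.4% corrected. With 14:7 evaluable and the corrected rule, per-type power is about 73% if all three respond and 61% if one does. That is 3/24 = 12.5% loss, slightly above the 10% at which the plan allows a sub-group to grow to 30.

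**6. Is there another reading?** Neither document describes a fourth primary hypothesis, a reserved share of alpha or a modified Hochberg. The combined endometriosis analysis in SAP 9.2.3 is labelled additional and lies outside the rule. SAP section 12 lists the dropped site adjustment and the randomisation ratio, not this.

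**The case against.** The written rule is explicit, the same in both documents, and conservative, so no false claim becomes more likely. Under the plan's own assumption of equal effects in all three types, correcting it gains only about a quarter of a point per type at 16:8. The 83% is labelled as the power of a single t-test at 5%, and for that it is right. Most of the fall from 83.7% to 64.7% in the one-responder case is the price of multiplicity (to 68.9%); the slip adds the last 4 points. The SAP text was written after the last patient's last visit, so restating power cannot change the sample size. The power figures also rest on simplifications: subjects can count in more than one type, the model is ANCOVA, missing scans are imputed, and randomisation is stratified by site and not by sub-group, so 12:12 within a type is not assured. Finally, the correction loosens a protocol-specified threshold late in the trial.

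All of this stands as a limit on size and on how the change must be made. None of it explains 0.0125 or removes the conflict between the named procedure and its steps. The timing is a reason to correct and document the threshold while the data are still blinded.

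**Conclusion.** The last threshold is wrong for the procedure both documents name: it should be 0.05/3 = 0.0167. Type I error is protected either way. The loss is about 4 points of power when one type responds, about 1 point when two do, and close to nothing when all three do. The 83% is arithmetically sound but does not describe the chance of success under the decision rule. With the corrected rule, that chance per type at 16:8 is about 81% if all three types respond and 69% if one does; at 12:12 it is about 86% and 75%. These power figures assume independent tests, t-tests in place of ANCOVA, 24 subjects per type and no drop-out. Overlap between types and the actual set sizes will move them. The threshold error itself depends on none of these assumptions.

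**What to change.** - In SAP 9.2.1 and Protocol 9.6.2, replace 0.0125 by 0.0167, written as 0.05/3, in both sentences where it appears (four places in all).
- Add a dated entry to SAP section 12 stating that the value was a slip for the named procedure and that the correction was made blind to treatment. The documents do not show whether the blind has since been broken. If it has, report the verdict under both thresholds and say so.
- In SAP 3.3, beside the 83%, give per-type power under Hochberg for 16:8 and for the 1:1 list: about 81% and 86% if all three types respond, about 69% and 75% if one does. State the independence and 24-per-type assumptions.

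The cost is wording and a documented change of a protocol-specified threshold. It needs no patients and no data, and the quoted power becomes less favourable where fewer than three types respond.

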9.2.2 Sensitivity Analyses

A number of sensitivity analyses are planned to establish robustness of the primary analysis, including summary statistics (expect for the placebo based MI in section 9.2.2.2). All sensitivity analysis except the PP analysis will be performed on the FAS.

9.2.2.1 Per Protocol Analysis

To test efficacy in more perfect conditions. For each type of lesion an analysis similar to the primary analysis will be performed using the PP population.

9.2.2.2 Missing Data

For each type of lesion three sensitivity analyses will be performed to investigate the impact of missing data, two completer analyses and one MI analysis:

Firstly, an ANCOVA analysis similar to the primary analysis, but without doing any imputation, and using only data from subject that have completed the scheduled treatment and have information from both the baseline and the cycle 4 MRI.

Secondly, a similar ANCOVA without imputation, using data from all subjects that have information from both the baseline and the end-of-treatment MRI.

Thirdly, a MI analysis will be performed using MI for missing data in a placebo-based pattern mixture model (based on a missing not at random (MNAR) condition). A MNAR assumption will be used as the primary analysis gives an unbiased estimation of the treatment effect under the MAR assumption.

This is done in 3 steps firstly initiating the process by imputing any non-monotone missingness using the MCMC method, just as in the primary analysis, the non-monotone missingness (missing at intermediate visits) is assumed to be MAR opposed to missingness due to drop-out which is assumed to MNAR. That is the non-monotone missingness is assumed to be unrelated to the medical condition, whereas the monotone missingness is allowed to depend on the medical condition. Secondly all monotone missingness is imputed, an approach, which imputes variables one at a time in the following order: NRS score at visit 2, at visit 5, at visit 6, at visit 7, and at visit 8, and finally the sum of lesion sizes at end-of-treatment, similar to the primary analysis, however this imputation will be based on only the placebo group. So the mean of the imputed values will be based on the mean of the placebo subjects with the same predictors as the subject that has missing

information. Thirdly the 100 imputations are analysed and combined similarly to the primary analysis.

